#### Missing and Partial AE end dates

- If end date is completely missing, end date is not imputed and the AE is flagged as “ongoing”
- If year is present and
  - month and day are missing
    - If year = year of last dose, then set end date to the date of last dose
    - If year < year of last dose, then set end month and day to December 31st
    - If year > year of last dose, then set end month and day to January 1st
  - month is missing
    - If year = year of last dose, then set end date to date of last dose
    - If year < year of last dose, then set end month to December
    - If year > year of last dose, then set end month to January
- If month and year are present and day is missing:
  - If year = year of last dose and

- month = month of last dose then set day to day of last dose
- month < month of last dose then set day to last day of month
- month > month of last dose then set day to 1st day of month
  - If year < year of last dose, then set end date to last day of the month
  - If year > year of last dose, then set end date to 1st day of month
- For all other cases, set end date to date of last dose

## 7. STUDY POPULATION

### 7.1. Overview of Planned Analyses

The analyses will be based on the SAF, unless otherwise specified. Table 9 provides an overview of the planned analyses and the associated study populations.

**Table 9: Overview of Planned Analyses and Study Populations Used**

Display Type	Data Displays Generated		
	Table	Figure	Listing
Subject disposition			
Total disposition	Y 		
Protocol deviations	Y 		Y
Summary of subjects in analysis population	Y		
Subjects excluded from each analysis populations			Y
Demographic Characteristics	Y 		Y
Baseline Characteristics	Y		Y
Medical History	Y		Y
Summary of Chronic Obstructive Pulmonary Disease History	Y		Y
Exposure	Y 		Y
Treatment Compliance	Y 		Y
Prior Medications	Y		Y
Concomitant Medications	Y		Y
Rescue Medications	Y		Y

NOTES :

- Y = Yes display generated
- [1]: Data from clinic or database
- [2]: Display will be based on the SAF
- [3]: Display will be based on the SAF and repeated for the FAS, PP and PKAS

### 7.2. Subjects Disposition

A clear accounting of the disposition of all subjects who enter the study will be provided, from screening to end of study participation. Summaries of subject disposition presented by treatment arm and overall, will be provided as follows:

- Number and percentage of subjects enrolled
- Number and percentage of subjects randomized
- Number and percentage of subjects in each of the SAF, FAS, PP, and PKAS
- Number and percentage of subjects who withdrew early from the study (including reasons for early withdrawal)

By-subject listings of enrollment details, randomization details, visit dates, and withdrawal details (including reason for discontinuation and duration of treatment prior to discontinuation) will also be provided.

### **7.3. Screen Failures**

Number and percentage of subjects who were screened for the study (enrolled subjects, ie, those who signed informed consent) and reasons for screen failure will be summarized.

### **7.4. Protocol Deviations**

Deviations from the protocol including violations of inclusion/exclusion criteria will be assessed as ‘minor’ or ‘major’.

Major deviations will lead to the exclusion of a subject from the PP population and the PKAS. Major deviations may lead to the exclusion of a subject from the PP population and the PKAS. Major protocol deviations and PP exclusions will be identified during the Blinded Data Review Meeting (BDRM) before database lock.

Major protocol deviations may include:

- Subjects who had their blinded randomization code broken.
- Subjects with overall treatment compliance <80% or >120%.
- Subjects who used prohibited medications (prior and/or concomitant) that may have significant influence on efficacy.
- Subjects who did not satisfy the inclusion/exclusion that may have significant influence on efficacy.
- Subjects not treated with the treatment assigned at randomization, but wrongly treated in another treatment group.

A summary of protocol deviations, major protocol deviations and exclusionary major protocol deviations will be produced by treatment arm as well as by type of deviation will be provided. In addition, a by-subject listing of protocol deviations will be provided.

### **7.5. Demographic Characteristics**

The following demographic characteristics will be summarized for subjects in the SAF, FAS, PP and PKAS populations by treatment arm:

- Age (years, as a continuous variable)
- Sex (Male, Female)
- Race

- Ethnicity
- Weight at screening (in kilograms)
- Height at screening (in centimeters)
- BMI at screening (in kg/m^2) calculated at screening
- Smoking Status at baseline
- Chest X-Ray, CT Scan at baseline
- Pregnancy Test at baseline
- COPD Exacerbation in the previous 3 months before screening at baseline

Age will be calculated as the number of complete years between a subject's birth date and the date of informed consent.

Age will also be summarized in the following categories: 40 <=65 years and >65-85 years. All demographic data will be listed by treatment and subject.

## **7.6. Listing of Subject Inclusion and Exclusion Criteria**

Subjects who failed any of the inclusion and exclusion criteria will be listed along with the reason. Any subject withdrawal during the study, along with the reason for withdrawal, will be documented in listings.

Failed inclusion/exclusion criteria and withdrawal data will be listed by treatment and subject.

## **7.7. Medical History and Medical Conditions Present at Entry**

Medical and surgical history, treatment history, current medical conditions and smoking status will be recorded at the Screening visit. Medical history will be coded by system organ class (SOC) and preferred term (PT) using the Medical Dictionary for Regulatory Activities (MedDRA™) Version 18.0 or later. Medical history data will be listed by treatment and subject.

## **7.8. Prior and Concomitant and Rescue Medication**

Any medication (including over-the-counter medications) or therapy administered to the subject during the study (other than the study drug/treatment, starting at the date of informed consent) is considered a concomitant medication. All concomitant medications must be recorded in the EDC system.

### **Rescue Medication(s)**

Albuterol/salbutamol MDI will be permitted throughout the study as rescue medication and will be dispensed to the subjects at Visit 2 or at the start of washout (if the subject requires washout) and at subsequent scheduled visits as required, for self-administration as needed, at home.

Subjects will be trained to abstain from using albuterol/salbutamol MDI, 6 hours prior to start of each visit. If this is not possible, the visit will need to be rescheduled. Any rescue medication(s) taken will be recorded in the subject diary and appropriate eCRFs. A summary showing the number of subjects who used rescue medication at any time post randomization (based on the information reported in the subject diary) and a descriptive summary of the amount of rescue medication used (based on the information reported in the subject diary) will be provided by treatment arm, as change as from baseline in daily and weekly averages. A by-subject listing of all rescue medication used, as reported on the patient diary, will also be provided.

All concomitant medication will be coded using World Health Organization Drug Dictionary (WHO-DD) 1 June 2009.

The following information must be recorded in the EDC system for each concomitant medication: preferred name or trade name, route of administration, start date, stop date, dose level, total daily dose, and indication. Any changes in the dosage or regimen of a concomitant medication must be recorded in the EDC system.

Medications will be assigned to a time period (prior and/or concomitant) as follows:

- If both the start and stop date exist and are before the first dose date of study drug, the medication will be counted as prior.
- If the start date is on or after the first dose date of study drug, the medication will be counted as concomitant.
- If the start date and stop date is on the first dose date of study drug, the medication will be counted as prior.
- If the start date is before the first dose date of study drug and the stop date is after the first dose date of study drug or the medication is continuing, the medication will be counted as prior and concomitant.
- If the start date is missing and the stop date is before the first dose of study drug, the medication will be counted as prior.
- If the start date is missing and the stop date is after the first dose of study drug or the medication is continuing, the medication will be counted as concomitant.
- If the start and stop dates are missing, the medication will be counted as concomitant.

Summaries showing number of subjects and percentage taking each medication will be provided for each preferred medication term by treatment arm. This will be done separately for prior and

for concomitant medications. A by-subject listing of all prior and concomitant medication data will also be provided.

### **7.9. Total Duration of Therapy, Average Daily Dose, Maximum Daily Dose, Final Daily Dose of Study Medication, and Compliance**

The number of subjects exposed to each study treatment will be summarized.

The number of days on treatment and the number of days on study (screening through to end of study/follow-up) will be summarized by study treatment.

Treatment compliance will be calculated (the total number of doses actually taken / total number of doses expected\*100). For subjects who have completed the study:

Study Period	Duration	Scheduled Doses	Compliance Criteria	
			Not less than 80% (doses)	Not more than 120% (doses)
Randomized Treatment	21 Days	21	17	25

For subjects who are early terminated, treatment compliance will be determined from their duration in the study, up to the time they are considered early terminated. Subjects taking fewer than 80% or more than 120% of the required doses will be considered non-compliant with dosing.

In addition, treatment compliance will be classified into four categories (<80%,  $\geq 80\% - \leq 100\%$ ,  $>100\% - <120\%$ ,  $\geq 120\%$ ). Treatment compliance will be summarized by category and study treatment.

## 8. PHARMACOKINETICS

### 8.1. Overview of Pharmacokinetic Analyses

The pharmacokinetic analyses will be based on the PKAS, unless otherwise specified. Table 10 provides an overview of the planned pharmacokinetic analyses.

**Table 10: Overview of Pharmacokinetic Analyses**

	Stats Analysis		Summary		Individual
	T	F	T	F	L
Plasma Concentrations on Day 1 and Day 21			Y	Y 	Y
Urine Concentrations on Day 1 and Day 21			Y	Y 	Y
Pharmacokinetic Parameters on Day 1 and Day 21			Y		Y
Primary Endpoints -PKAS					
Peak concentrations during the dosing interval at steady-state (C maxSS )	Y 		Y	Y	
Area under the plasma concentration-time curve over the dosing interval at steady state (AUC 0-<math>\tau</math>SS )	Y 		Y	Y	
Exploratory Analysis	Y 	Y 			

NOTES :

- T = Table, F = Figure, L = Listing, Y = Yes display generated.
- Stats Analysis = Represents TF related to any formal statistical analyses (ie modeling) conducted.
- Summary = Represents TF related to summaries (ie descriptive statistics) of the baseline, post-treatment and change from baseline for the primary pharmacodynamics analyses method.
- Individual = Represents L related to any displays of individual subject observed raw data.
- [1] = mean graph and semi-log graph by treatment on Day 1 and Day 21; A spaghetti plot for plasma concentration
- [2] =ANOVA applied ; [3]= Power Model applied; [4] = Spaghetti plot and dose-proportionality plots for plasma and urine parameters

### 8.2. Presentation of PK Data, Descriptive Statistics and PK Assessment

Pharmacokinetic plasma and urine concentration data will be listed by treatment, subject, day and actual sampling times relative to dosing for plasma data. Plasma and urine concentrations will be summarized by treatment, day and nominal time point. The following descriptive statistics will be presented for plasma and urine concentrations obtained at each nominal time point: n, arithmetic mean, SD, coefficient of variation (%CV), geometric mean, median, minimum and maximum values, where %CV =  $100 \times \text{SD}/\text{mean}$ .

Plasma and urine pharmacokinetic parameters will be listed by treatment, subject and day and summarized by treatment and day. Descriptive statistics for calculated PK parameters will include: n, arithmetic mean, SD, %CV, geometric mean, geometric mean %CV, median, minimum and maximum values, where geometric mean %CV is the standard deviation of

logarithm of data expressed in anti-logarithmically as a percent (ie  $100 \times \sqrt{\exp(SD^2) - 1}$ ). For  $t_{\max}$  and  $t_{\text{last}}$ , only median, minimum and maximum values will be presented. No descriptive statistics will be determined when fewer than three individual PK parameters are available.

Combined individual plasma concentrations versus actual times will be plotted by treatment and day (spaghetti plots).

For doses of GSP304, the arithmetic mean plasma concentration versus nominal times will be presented overlaid with the arithmetic mean profile of Spiriva® Respimat® by day both on linear and semi-logarithmic scales.

The following rules will be followed with regards to the number of decimal places and presentation of data in the tables and listings of concentration data:

- The individual concentrations will be reported to the same precision as the source data (for example, if the source data is presented to five significant digits, the individual values will be presented to five significant digits);
- The mean, SD, geometric mean and median will be tabulated to one more significant digit compared to the source data, but with a maximum of four significant digits;
- Minimum and maximum values will be tabulated to the same precision as the source data, but with a maximum of four significant digits;
- Coefficient of variation (%CV) and geometric coefficient of variation will be presented to one decimal place.

The following rules will be followed with regards to the number of decimal places and presentation of data in the tables and listings of PK parameters:

- Individual PK parameters will be presented to four significant digits, with the exception of  $t_{\max}$ , which will be presented to two decimal places. In addition, parameters directly derived from source data (eg  $C_{\max}$ ) shall be reported with the same precision as the source data (if this is not four significant digits);
- The mean, geometric mean, median and SD values will be reported to four significant digits, all other descriptive statistics will be reported to three significant digits except for %CV and the geometric %CV, which will be presented to one decimal place. For  $t_{\max}$  the minimum and maximum will be presented to two decimal places and the rest of the descriptive statistics to three decimal places;
- Estimates and confidence intervals in the form of percentages will be presented to two decimal places.

Source data shall be used in all derived PK parameter calculations without prior rounding.

### **8.3. Statement of the Null and Alternative Hypotheses**

No formal hypothesis testing will be conducted for the primary pharmacokinetic endpoints.

### **8.4. Analysis of the Primary Pharmacokinetic Endpoints**

The primary endpoint,  $AUC_{0-\text{tauSS}}$ , and  $C_{\text{maxSS}}$ , will be analyzed using an analysis of variance (ANOVA) model. An ANOVA will be performed on the ln-transformed  $AUC_{0-\text{tauSS}}$ , and  $C_{\text{maxSS}}$ . The ANOVA model will include treatment as fixed effect. The results from the model will be back-transformed and the adjusted geometric means for each treatment and the estimated treatment ratios for the treatment comparisons will be presented together with 90% CIs. The ratios and corresponding 90% CIs will be expressed as a percentage. The following comparisons will be made:

- GSP304 █ vs Spiriva® Respimat®
- GSP304 █ vs Spiriva® Respimat®
- GSP304 █ vs Spiriva® Respimat®

The statements of a SAS® PROC MIXED analysis would be:

```
PROC GLIMMIX data=dataset;
  CLASS subject dose;
  MODEL log_normliased_pk_parameter= dose / ddfm=kr link=log;
  RANDOM intercept /subject= subject;
  ESTIMATE 'GSP1 vs Spiriva' dose 1 0 0 -1 /cl alpha=0.1;
  ESTIMATE 'GSP2 vs Spiriva' dose 0 1 0 -1 /cl alpha=0.1;
  ESTIMATE 'GSP3 vs Spiriva' dose 0 0 1 -1 /cl alpha=0.1;
  LSMEANS dose/diff cl ilink alpha=0.10
RUN;
```

The back-transformed and adjusted means for each treatment and the estimated treatment differences for the treatment comparisons will be presented together with 90% confidence intervals for the treatment comparisons. The adjusted means and estimated treatment differences for the treatment comparisons will also be plotted, with corresponding 90% confidence intervals.

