## 4. STUDY DESIGN

### 4.1. Summary of Study Design

This is a phase 2, randomized, parallel group, active-and placebo-controlled, 5-arm study to compare the PK profile of 3 blinded doses of GSP304 with open label Spiriva® Respimat®. The study will also evaluate the dose response PD profile of 3 blinded doses of GSP304 compared with blinded GSP304 placebo, using spirometry in subjects with mild to moderate COPD.

The study will consist of a screening period of up to 2 weeks, followed by a 2-week run-in period, a 3-week treatment period, and a 2-week post treatment follow-up period. The total duration of study participation will be approximately 9 weeks.

A total of 155 male and female subjects will be randomized in a 1:1:1:1:1 ratio to 1 of 5 treatment arms. A subject will receive 1 of the 3 double-blind doses of GSP304, or double-blind GSP304 placebo, or open-label Spiriva® Respimat®.

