#### **6.5.4. Pharmacokinetic Set (PKAS)**

This will include all subjects who are randomized, received at least 1 dose of study treatment and have at least 1 quantifiable PK sample and do not have exclusionary major protocol deviations. The PKAS will be used to analyze the PK endpoints unless otherwise specified in this SAP. Major and exclusionary protocol deviations will be defined in section 7.3 and by clinical review prior to unblinding.

Subjects or data may be excluded from the PKAS at the discretion of the PK Scientist upon consultation with the sponsor. Any data excluded will be discussed in the CSR. Any excluded subject will have his or her concentration and PK parameter data (if available) listed only. Subjects who receive placebo will not be part of the PKAS. The PKAS will be used for all tables and graphical summaries of the PK data

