- $A_{\tau_{avSS}}$  is the cumulative amount excreted over the dosing interval and will be calculated as the sum of the products of concentration and urine volume over the appropriate collection intervals. For the calculation of urine PK parameters the protocol time intervals should be used. If a subject urinates into the toilet or a urine sample is lost any other way, or if no urine volume has been recorded for a sampling interval, the cumulative amount excreted starting with this interval cannot be calculated. If, however, a subject is unable to urinate, no amount excreted has been lost and the cumulative amount can continue to be calculated past that collection interval. For the affected time interval, the partial amount will be zero;
- $Fe\%$  is the fraction of unchanged drug in urine expressed as a percentage and will be calculated as  $Fe\% = (A_{\tau_{avSS}} / Dose) * 100$ .

If  $t_{last}$  (last time point with measurable concentration) is before 24 hour post-dose in more than

50% of treated subjects s at any particular dose of GSP 304 or Spiriva® Respimat®, AUClast (area under the plasma concentration time curve from time zero to last time point with measurable concentration) may be estimated and compared between different doses of GSP 304 and Spiriva® Respimat® by ANOVA.

Any inconsistency between plasma and urine PK would be will be further investigated and might be flagged and/or excluded from the analysis at the discretion of the PK Scientist after consultation with the sponsor.

An exploratory PK/ glomerular filtration rate (GFR) analysis of GSP304 in urine and plasma may be performed if deemed appropriate following review of the summary PK and GFR data. The decision to perform this analysis will be made by the Sponsor upon review of the tables, figures and listings produced at the end of the study. If the decision is made not to proceed with the PK/ GFR analysis, this section of the SAP will not be applicable and the outputs described herein will not be presented.

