#### **10.4. Laboratory Data**

Baseline and post-baseline clinical laboratory data (hematology, biochemistry, liver function, and urinalysis), will be summarized for Visit 4 to Visit 7 (the Final Visit). Descriptive statistics (number of subjects, mean, SD, median, minimum and maximum) will be presented for laboratory data as well as change from baseline by treatment and visit. In addition, values outside the respective normal range and values deemed as clinically significant by the Investigator will be listed.

The number of subjects with values of potential clinical significance determined by the investigator will be tabulated by treatment group and visit.

Shift tables will present changes from baseline in laboratory data (categorized as normal; abnormal, not clinically significant; and abnormal, clinically significant) to end of treatment.

All laboratory data will be listed by treatment and subject.

Estimated Glomerular filtration rate (eGFR) will be estimated using the Cockcroft-Gault approach.

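### Pre-specifying screening eGFR as a covariate in the primary PK model would be a cheap, conditional gain in precision; the treatment-only ANOVA is valid as it stands

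*SAP*

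**What the plan says.** The SAP describes the trial as follows (section 4.1): "This is a phase 2, randomized, parallel group, active-and placebo-controlled, 5-arm study". The primary PK parameters are ln-transformed and compared between each GSP304 dose and Spiriva Respimat. Section 8.4 specifies the model in one sentence, "The ANOVA model will include treatment as fixed effect", and says that "the estimated treatment ratios for the treatment comparisons will be presented together with 90% CIs". The sample code there also has dose as its only fixed effect, and the footnote to Table 14.2.5 agrees. Section 8.3 adds: "No formal hypothesis testing will be conducted for the primary pharmacokinetic endpoints". Four arms enter the model, because "Subjects who receive placebo will not be part of the PKAS" (section 6.5.4).

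On renal function, section 4.5 schedules biochemistry at screening, and Table 4 makes screening the baseline for laboratory values. The shell for Table 14.3.5.1.1 lists serum creatinine and GFR. Section 10.4 names the method: "Estimated Glomerular filtration rate (eGFR) will be estimated using the Cockcroft-Gault approach". The only link to PK is in section 6.7.6.2: "An exploratory PK/ glomerular filtration rate (GFR) analysis of GSP304 in urine and plasma may be performed". The sponsor decides whether to do it after seeing the end-of-study tables, figures and listings.

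**The concern.** A parallel-group comparison has no within-subject contrast, so differences between people in drug exposure go straight into the error term of every GSP304/Spiriva ratio. With no formal PK test, the 90% interval is the whole primary PK result. The 28 subjects per arm were derived for FEV1. Section 4.3.1 only asserts that this number suffices for relative bioavailability and gives no coefficient of variation or target width.

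Against that background, a pre-randomization measurement that may explain part of the exposure variance is left out of the model. If it is brought in after the ratios have been seen, it can only serve as exploration. If it is named beforehand, it can support the primary estimate. By contrast, the primary FEV1 model in section 9.6.1 does adjust for baseline and center.

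**Working it through.** **Sample size, reproduced first.** The SAP gives no PK precision figure to check. Its 28 per arm rests on a 150 mL difference, SD 170 mL, two-sided 5% and 90% power for FEV1 (section 4.3.1). A two-sample noncentral t calculation gives power 0.889, 0.900 and 0.910 at n = 27, 28 and 29, so 28 reproduces. I carry 28 per arm into the PK model; the number evaluable for PK may differ.

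**Inputs.**
- From the SAP: four arms, 28 per arm and a 90% interval. Error degrees of freedom are 4 × 28 − 4 = 108, or 107 with one covariate.
- Assumed, because the SAP gives neither: the between-subject CV of exposure, and r, the within-arm correlation of ln(eGFR) with ln exposure.

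**Formulas, ln scale**, with s = √ln(1 + CV²):
- Treatment only: h0 = t(0.95, 108) × s × √(2/28).
- With the covariate: h1 = t(0.95, 107) × s × √(1 − r²) × √(2/28) × √(1 + 1/106). The last term is the expected cost of chance imbalance in the covariate.
- Ratio: h1/h0 = (1.65922/1.65909) × √(107/106) × √(1 − r²) = 1.0048 × √(1 − r²). This does not depend on the CV.

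**Treatment-only interval.** At an assumed CV of 50%, s = 0.472 and h0 = 1.6591 × 0.472 × 0.2673 = 0.2095. The interval is therefore the point estimate divided and multiplied by exp(0.2095) = 1.233. For a true ratio of 100% this is 81.1% to 123.3%. The same calculation gives 87.8% to 113.9% at CV 30% and 73.2% to 136.6% at CV 80%.

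**Effect of the covariate:**

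| r | √(1 − r²) | h1/h0 | Change in ln-scale width | 90% CI factor at CV 50% |
|---|---|---|---|---|
| 0 | 1.000 | 1.005 | +0.5% | 1.234 |
| 0.1 | 0.995 | 1.000 | 0% | 1.233 |
| 0.2 | 0.980 | 0.984 | −1.6% | 1.229 |
| 0.3 | 0.954 | 0.959 | −4% | 1.222 |
| 0.4 | 0.917 | 0.921 | −8% | 1.213 |
| 0.5 | 0.866 | 0.870 | −13% | 1.200 |

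Break-even is at r² of about 0.0095, so r is about 0.1. Before the covariate cost, 28/(1 − r²) gives the equivalent of about 31, 33 and 37 subjects per arm at r = 0.3, 0.4 and 0.5.

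**Chance imbalance.** The standardized difference in mean ln(eGFR) between two arms has SD √(2/28) = 0.267. At CV 50%, a one-SD imbalance shifts the unadjusted ratio by exp(r × 0.472 × 0.267): about 4% at r = 0.3 and 6.5% at r = 0.5. The adjusted model corrects this shift in the realized sample. It is another view of the same precision gain and should not be counted twice.

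**The case against.** The strongest reply is that nothing here is defective. A treatment-only ANOVA on the ln scale is fully pre-specified, and the text and table footnote agree on it. With no PK test, acceptance limits or target width, no planned decision turns on a slightly narrower interval. That stands, and it limits the point to an improvement.

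A reader might infer three stronger claims, and the documents support none of them:

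- **That the plan regards renal function as an established determinant of exposure.** Section 6.7.6.2 only permits an exploration if it is deemed appropriate, and section 8.5 gives duration of nebulization similar optional treatment. Measuring urinary excretion as a secondary endpoint does not show that eGFR explains variation in plasma AUC or Cmax.
- **That omitting eGFR biases the ratios.** Under randomization the unadjusted ln-ratio is unbiased. Chance imbalance is sampling variation that the interval already covers.
- **That the intervals are certainly wider than they need be.** The SAP gives no correlation. Up to r = 0.2 the gain is under 2%, and at r = 0 there is a small loss. Nothing in the SAP supports one r for both AUC0-tauSS and CmaxSS.

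Two further cautions also stand. Creatinine drawn between Day −28 and Day −15 is about five to seven weeks old by Day 21, which may weaken r. Any renal eligibility limits in the protocol, which is not at hand, would narrow the eGFR range and weaken r further. Finally, the late decision in section 6.7.6.2 concerns an exploratory output and does not leave the primary model open.

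**Conclusion.** The point holds as a cheap improvement. The section 8.4 model is valid but makes no use of a baseline value that is already collected and that the plan itself singles out for possible PK exploration. Including it changes the ln-scale interval width by between +0.5% (r = 0) and −13% (r = 0.5), with break-even near r = 0.1. The expected loss is small and bounded, while the possible gain is moderate, so the trade favours adjustment.

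The size rests on an assumed r, on 28 PK-evaluable subjects in each of four arms and on a common slope across arms. The interval factors also assume a CV of 50%. Section 9.3 allows extra covariates, but it sits in the pharmacodynamics section and acts only once an imbalance has been seen, so it does not settle the matter.

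**What to change.** Before unblinding, amend section 8.4 so that ln AUC0-tauSS and ln CmaxSS are each analysed by a linear model with treatment and ln(screening Cockcroft-Gault eGFR) as fixed terms. Report the adjusted geometric mean ratios with 90% intervals, and show the treatment-only ANOVA as supportive. The PK/GFR exploration in section 6.7.6.2 can remain as an additional output.

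The covariate should go into an ordinary linear model on the ln scale. The sample code, "MODEL log_normliased_pk_parameter= dose / ddfm=kr link=log", applies a log link to a response whose name suggests it is already logged, and it adds a random subject intercept although each subject contributes one value per parameter. It needs correcting to match the stated ANOVA before a term is added.

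The cost is one degree of freedom, the code and footnote changes, and the loss from the adjusted model of any subject without a screening creatinine, which should be almost none. No new data are required.
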